## **9.8 Safety Follow-up Visits**

### **9.8.1 Days ( $\pm 4$ ) 42 and 56/EOF**

Subjects will be followed-up by virtual visits (eg, telephone or video contact) on Days ( $\pm 4$ ) 42 and 56 to determine the following safety parameters:

- Hospitalization status (yes, no)

- Intubation status (yes, no)
- Survival (yes, no)

Responses can be provided by caregivers.

Subjects will also be assessed for COVID-19 symptoms, as well as any adverse events that were ongoing at the previous visit (ie, adverse events ongoing on Day 28 will be followed up on Day 42; adverse events ongoing on Day 42 will be followed up on Day 56).

## **9.9 Clinical Laboratory Evaluations**

All laboratory parameters will be processed at a local laboratory. Each of the laboratory parameters to be evaluated during the study (including clinical chemistry, hematology, and urinalysis) and the corresponding collection times are detailed in the Event Schedule (see [Section 5.1](#)). Detailed instructions regarding sample collection and processing are provided in the laboratory manual.

## **9.10 Clinical Procedures and Observations**

Investigators/study staff will regularly monitor subjects throughout study participation.

### **9.10.1 Medical History**

A complete medical history, including documentation of COVID-19 diagnosis, will be obtained at Screening.

### **9.10.2 Concomitant Medications**

All medications being taken concomitantly by the subject at Screening will be recorded. All concomitant medications taken by the subject from Day 1 through Day 28 will be recorded, including the use of antipyretics and vasopressors or inotropes.

### **9.10.3 Physical Examination**

Physical examinations will be performed by the Investigator or designee whose license permits the performing of physical examinations at the timepoints defined in the Event Schedule (see [Section 5.1](#)). A physical examination, including calculation of body mass index, should be performed at Screening. Starting on Day 7, physical examination will be symptom-directed visual inspection; the physical exam will be a virtual exam on Days 7, 14, and 21. The physical exam should be conducted in person on Day 28, but may be conducted virtually.

### **9.10.4 Vital Signs**

Vital signs (blood pressure, pulse rate, SpO2, FiO2, and body temperature) will be collected throughout the study at the timepoints defined in the Event Schedule (see [Section 5.1](#)).

### **9.10.5 COVID-19 Signs and Symptoms**

Signs and symptoms of COVID-19, including any laboratory abnormalities, will be documented at Screening and on Days 7, 14, 21, and 28. Symptoms of COVID-19 will

also be assessed on Days 42 and 56. Any new or worsening of signs/symptoms of COVID-19, including any laboratory abnormalities, should be attributed to COVID-19 and should not be reported as adverse events or serious adverse events.

#### **9.10.6 COVID-19 Complications**

Complications of COVID-19, including any laboratory abnormalities, will be documented on Days 7, 14, 21, and 28. Any new or worsening of complications of COVID-19, including associated laboratory abnormalities, should be attributed to COVID-19 and should not be reported as adverse events or serious adverse events.

#### **9.10.7 Severity of COVID-19 (8-Point WHO Ordinal Clinical Scale)**

The severity of COVID-19 will be assessed using the following 8-point WHO Ordinal Clinical Scale at the timepoints defined in [Section 5.1](#). The scale measures the clinical status of a subject at the first assessment of a given day.

- 1) Ambulatory (not hospitalized), no limitation of activities;
- 2) Ambulatory (not hospitalized), limitation of activities;
- 3) Hospitalized, no oxygen therapy;
- 4) Hospitalized, oxygen by mask or nasal prongs;
- 5) Hospitalized, non-invasive ventilation or high-flow oxygen;
- 6) Hospitalized, intubation and mechanical ventilation;
- 7) Hospitalized, ventilation plus additional organ support – vasopressors (pressors), renal replacement therapy (RRT), extracorporeal membrane oxygenation (ECMO);
- 8) Death.

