## 5 EVENT SCHEDULE

### 5.1 Event Schedule – All Subjects

Procedure	Timepoint	Hospitalization			Inpatient or Outpatient Visits†				Safety Follow-up Visits	
		Phase	Screening *	Dosing *	Post-Dosing	Day 7 ± 1	Day 14 ± 1	Day 21 ± 1	Day 28 ± 1/ EOS	Day 42 ± 4
		Day 0 Pre-Dose	Day 0/1 Dose	Day 1 Post-Dose						
Informed Consent Form		X								
Eligibility Criteria		X								
Demographic Data		X								
Medical History 		X								
COVID-19 Signs and Symptoms		X		X	X	X	X	X	X 	X 
COVID-19 Complications				X	X	X	X	X		
Prior/Concomitant Medication		X			X	X	X	X		
Physical Examination		X			X 	X 	X 	X 		
Body Mass Index		X								
Vital Signs 		X		X	X	X	X	X		
Urine Pregnancy Test 		X								
Severity of COVID-19 (Ordinal Clinical Scale) 		X		X	X	X	X	X	X	X
Clinical Chemistry 		X							X 	
Serum Troponin I		X								
Hematology 		X							X 	
Urinalysis 		X							X	
Randomization			X							
Study Drug Administration 			X							
Adverse Events				X	X	X	X	X	X 	X 
Safety Follow-up									X 	X 

Coronavirus disease 2019 = COVID-19; EOF = end of follow-up; EOS = end of study

Note: Hospital can also refer to controlled facility such as an emergency room, urgent care facility, temporary/modular hospital, infusion center, clinical research unit, etc.

\* No more than 24 hours can elapse between screening and dosing with RBT-9.

† Day 7, 14, and 21 will be virtual visits; the Day 28 visit should be in person, but may be conducted virtually.

- 1 Medical history must include documentation of COVID-19 diagnosis.
- 2 On Days 42 and 56, COVID-19 symptoms (not signs) will be solicited.
- 3 Starting on Day 7, physical examination will be symptom-directed visual inspection.
- 4 Vital signs include assessment of blood pressure, pulse rate, oxygen saturation ( $\text{SpO}_2$ ), fraction of inspired oxygen ( $\text{FiO}_2$ ), and temperature.
- 5 Pregnancy testing is to be performed in female subjects of childbearing potential.

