- 6 Severity of COVID-19 will be assessed by the 8-point WHO Ordinal Clinical Scale, which includes: 1. Ambulatory (not hospitalized), no limitation of activities; 2. Ambulatory (not hospitalized), limitation of activities; 3. Hospitalized, no oxygen therapy; 4. Hospitalized, oxygen by mask or nasal prongs; 5. Hospitalized, non-invasive ventilation or high-flow oxygen; 6. Hospitalized, intubation and mechanical ventilation; 7. Hospitalized, ventilation plus additional organ support – vasopressors (pressors), renal replacement therapy (RRT), extracorporeal membrane oxygenation (ECMO); 8. Death. The Ordinal Clinical Scale is the clinical status at the first assessment of a given study day.
- 7 Parameters include: total protein, albumin, bicarbonate, blood urea nitrogen, serum creatinine, total bilirubin, alkaline phosphatase, glucose, sodium, potassium, phosphorus, calcium, magnesium, gamma-glutamyl transferase, alanine aminotransferase, aspartate aminotransferase, and ferritin.
- 8 Clinical chemistry and hematology are optional on Day 28.
- 9 Parameters include: hemoglobin, hematocrit, leukocytes with differential (absolute), and platelets.
- 10 Parameters include pH, specific gravity, protein, glucose, nitrite, ketones, WBC esterase, and occult blood.
- 11 Administer study drug after all pre-dose evaluations have been completed.
- 12 Adverse events that are ongoing on Day 28 will be followed on Day 42; adverse events that are ongoing on Day 42 will be followed on Day 56.
- 13 Safety follow-up assessment will be conducted virtually by telephone or video contact to determine the following: hospitalization status (hospitalized: yes, no), intubation status (intubated: yes, no), and survival (alive: yes, no).

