### **9.3 Study Design**

This is a Phase 2, randomized, placebo-controlled, multicenter study that will evaluate the efficacy, tolerability, and safety of a single dose of RBT-9 on the progression of COVID-19 infection in non-critically ill adults who are at high risk due to age and/or comorbid conditions. Subjects with documented SARS-CoV-2 infection who are at high risk for disease progression, as defined in the inclusion criteria (see [Section 9.1](#)), and require observation and/or treatment in a hospital will be screened for entry into the study. Eligible subjects will be stratified by time since COVID-19 diagnosis (<48 hours,  $\geq$ 48 hours) and randomly assigned in a 2:1 ratio to receive a single intravenous infusion of 90 mg RBT-9 or placebo (normal saline). No more than 24 hours can elapse between Screening and Dosing of RBT-9.

All subjects will be assessed through Day 56. All subjects, regardless of hospitalization status, will be assessed on Days 7, 14, 21, and 28, according to the Event Schedule (see [Section 5.1](#)). Assessments will include severity of COVID-19 measured by the 8-point WHO Ordinal Clinical Scale, physical examination, vital signs, clinical laboratory evaluations, concomitant medications, and adverse events. For subjects who have been discharged from the hospital, visits on Days 7, 14, and 21 will be conducted virtually (eg, by telephone or video contact). The Day 28 visit should be conducted in person, but may be conducted virtually, as well. Subjects will also be assessed at safety follow-up visits, which will be conducted virtually (eg, by telephone or video contact) on Days 42 and 56.

An independent data and safety monitoring board (DSMB) will actively monitor interim data to make recommendations regarding study conduct/continuation. The DSMB will meet once the first 30 subjects complete the Day 7 assessment to perform the first interim analysis of the safety data. Enrollment of 30 additional subjects will proceed if the safety profile of RBT-9 is deemed acceptable (as determined by the DSMB). Two additional DSMB interim analyses will be performed once 60 and 90 subjects complete the Day 7 evaluation. The last DSMB interim analysis will be performed once 150 subjects complete the Day 28 evaluation; sample size re-estimation will also be performed to allow a sample size increase to 252 subjects based on pre-defined conditional power rules.

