#### **11.1 Endpoints**

The following efficacy endpoints are defined for the study.

Primary Endpoint: Percentage of subjects in each treatment group in categories 4 through 8 of the 8-point WHO Ordinal Clinical Scale through Day 28.

Secondary Endpoints:

- Time to first occurrence of either death from any cause or new/worsened organ dysfunction through Day 28, defined as at least one of the following:
  - Respiratory decompensation
  - New or worsening congestive heart failure
  - Requirement of vasopressor therapy and/or inotropic or mechanical circulatory support
  - Ventricular tachycardia or fibrillation lasting at least 30 seconds and/or associated with hemodynamic instability or pulseless electrical activity, or resuscitated cardiac arrest

- Initiation of renal replacement therapy.
- Percentage of subjects who are alive at Day 28.
- Among subjects who begin oxygen therapy, mean change from initiation to last day on oxygen or Day 28 (whichever happens first) in SpO2/FiO2 ratio.
- Percentage of subjects with fever through Day 28.
- Percentage of subjects who develop AKI, as determined by the Investigator, through Day 28.
- Percentage of subjects with new or worsening congestive HF through Day 28.
- Percentage of subjects with ventricular tachycardia or fibrillation lasting at least 30 seconds and/or associated with hemodynamic instability or pulseless electrical activity, or resuscitated cardiac arrest through Day 28.
- Percentage of subjects who remain hospitalized at Day 28.
- Length of hospitalization through Day 28.
- Number of oxygen-free days through Day 28.
- Percentage of subjects transferred to the ICU through Day 28.
- Number of days on mechanical ventilation through Day 28.
- Time to and duration of vasopressor or inotrope utilization through Day 28.
- Percentage of subjects who begin dialysis through Day 28.

Exploratory Endpoints:

- Duration of COVID-19 symptoms through Day 56

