## 11.3 Data Analysis

The primary efficacy endpoint will be mapped to a binary endpoint (% categories 4-8) and then will be analyzed using a two-sided Fisher Exact test and using a logistic regression model to control for the stratification factors; the method of Firth will be used to predict outcomes. A two-sided Wilcoxon rank sum test will be used to compare the primary efficacy endpoint distributions for the two treatment groups. Continuous endpoints will be evaluated using a mixed model repeated measures (MMRM) analysis using a compound symmetry (CS) error structure. Time to event outcomes (eg, extubation, WHO progression, death) will be displayed using a Kaplan-Meier (KM) lifetable and treatment distributions compared using a stratified log-rank test and Cox proportional hazards model to control for time since COVID-19 diagnosis.

When appropriate, summary statistics will be provided (number of non-missing values, mean, median, standard deviation, minimum, and maximum for continuous variables and number and percentage of patients for categorical variables) by treatment group for all measures, including demographic and baseline assessments, safety, and efficacy endpoints. Baseline for all safety and efficacy endpoints is defined as the last observations before administration of study drug. No imputation will be used for missing data.

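### The primary endpoint claims to cover failure through Day 28, but the WHO scale is scored after dosing only on Day 1 and Days 7, 14, 21 and 28, and no rule covers the time between visits

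*Combined protocol and SAP*

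**What the plan says.** Section 11.1 defines the primary endpoint as "Percentage of subjects in each treatment group in categories 4 through 8 of the 8-point WHO Ordinal Clinical Scale through Day 28". Section 11.3 reduces this to a binary outcome. It does not say how several scores per subject become one result.

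The Event Schedule (Section 5.1) places the scale at Screening, Day 1 post-dose, Days 7, 14, 21 and 28, and then Days 42 and 56. Section 9.7.3 confirms the Day 1 post-dose score. Section 9.3 says that all subjects, "regardless of hospitalization status, will be assessed on Days 7, 14, 21, and 28". No daily inpatient score is scheduled. Section 9.10.7 makes each score a point-in-time reading: "The scale measures the clinical status of a subject at the first assessment of a given day". The Event Schedule footnote repeats the rule: "The Ordinal Clinical Scale is the clinical status at the first assessment of a given study day". There is no look-back, no worst-since-last-visit score and no rule for combining visits.

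Two other parts of the plan bear on this. Section 11.1 lists "Number of oxygen-free days through Day 28" among the secondary endpoints, with days on mechanical ventilation and length of hospitalization, all of which need dated information from between visits. The Event Schedule has no row for oxygen use, and nothing links such data to the primary endpoint. Section 9.1 admits subjects with saturation of 90 to 95% whether or not they are on supplemental oxygen, so category 4 at entry is possible.

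**The concern.** The endpoint's name promises coverage of a period, but the measurement rule covers five moments after dosing. A subject on oxygen from Day 2 to Day 6 who is off it or discharged by Day 7 has had the event the endpoint names, yet has no score that records it. The analysis would then estimate status on a few fixed days, not failure through Day 28.

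The gap falls at an important time. Section 6.2 expects the drug's anti-inflammatory shift within 24 to 48 hours, so Days 2 to 6 are when a difference could first appear. The interim looks at 60 and 90 subjects (Section 11.7) use Day 7 completers, whose only assured post-dose scores are Day 1 and Day 7, and the 10% conditional-power futility rule applies to them. Treatment is also open-label (Sections 9.6 and 10.5), so an outcome that depends on whether oxygen is running at one known moment each week is more exposed to discretion than one built from dated episodes.

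**Working it through.** **Inputs from Section 11.6.** Placebo n1 = 84, RBT-9 n2 = 168, two-sided alpha 0.045. Failure rates are 25% v 10%, 32% v 15% and 38% v 20%. Stated power is 84, 85 and 84%.

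**Step 1: reproduce the stated power.** Two-group chi-square with pooled variance under the null:

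power = Φ[(|π1 − π2| − z·SE0) / SE1], with z = 2.005.

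For 25% v 10%:
- pooled rate = (84 × 0.25 + 168 × 0.10)/252 = 0.15
- SE0 = √[0.15 × 0.85 × (1/84 + 1/168)] = 0.0477
- SE1 = √[0.25 × 0.75/84 + 0.10 × 0.90/168] = 0.0526
- power = Φ[(0.15 − 2.005 × 0.0477)/0.0526] = Φ(1.03) = 84.9%

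The three scenarios give 84.9, 85.6 and 84.6%, so the table is sound on its own inputs. The planned test is Fisher's exact test, whose exact power is 83.6, 84.0 and 82.5%. That is the reference below.

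**Step 2: sensitivity to missed episodes, equal in both arms.** Assume the table's rates are any-time rates and the scheduled scores catch a fraction c of failures in each arm. Both rates are multiplied by c. The documents give no value for c.

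| c | Rates, scenario 1 | Fisher power, scenarios 1 / 2 / 3 |
|---|---|---|
| 1.00 | 25.0% v 10.0% | 83.6 / 84.0 / 82.5% |
| 0.90 | 22.5% v 9.0% | 78.4 / 78.5 / 77.1% |
| 0.80 | 20.0% v 8.0% | 72.0 / 72.5 / 70.3% |
| 0.69 | 17.3% v 6.9% | 63.9 / 64.9 / 61.8% |

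The last row comes from a simple model. A share s of failures is always seen (deaths, long stays). The rest have one oxygen episode that starts uniformly within a 7-day interval and has exponential length with mean m days. Then c = s + (1 − s)(m/7)(1 − e^(−7/m)). With s = 1/3 and m = 5, c = 0.333 + 0.667 × 0.538 = 0.692. Other assumed values give a wide range: s = 0 and m = 3 gives c = 0.39 and power of 34–39%; s = 1/2 and m = 7 gives c = 0.82 and power of 71–73%.

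**Step 3: relax equal capture.** Keep s = 1/3 and a placebo mean of 5 days, and shorten the RBT-9 mean. Power is 69–71% at 4 days, 74–78% at 3 days and 82–87% at 2 days.

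**Step 4: subjects already on oxygen.** Suppose a share b is on oxygen at the Day 1 score and counts as a failure in both arms, with the table's rates applying to the rest. Each rate becomes b + (1 − b)π. At b = 0.10, scenario 1 becomes 32.5% v 19.0%, and Fisher power is 61, 66 and 68%. At b = 0.20 it is 43, 52 and 56%. The share b is also an assumption.

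**The case against.** The strongest reply is that the misclassification is not fixed in the text. Section 11 defers data handling to a separate Statistical Analysis Plan, which is not in the material reviewed. The secondary endpoints need between-visit oxygen data, and those data could be used for the primary endpoint. That is fair as far as it goes, but nothing says they will be. The only scoring rule given is the first assessment of the day at scheduled visits, and under that rule the between-visit episode is lost.

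Three stronger readings are tempting, and the documents do not support them.

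- A reader might infer that the assumed failure rates and the 84–85% power will not be reached. Section 11.6 gives no source for its rates and does not say whether they are any-time or visit-based. If they are visit-based, Step 2 does not apply and power is unchanged.
- A reader might infer that snapshots must lower event rates and cost power. Step 3 shows that the cost largely disappears if RBT-9 shortens episodes. Step 4 shows that subjects on oxygen at Day 1 push observed rates up, not down.
- A reader might infer that moving to a worst-day definition restores the stated power. It does not do so alone, because subjects still on oxygen after dosing would then be automatic failures in both arms, as they already are if the Day 1 score counts.

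**Conclusion.** The mismatch between endpoint and measurement stands. The endpoint is worded as "categories 4 through 8 of the 8-point WHO Ordinal Clinical Scale through Day 28", yet scoring at five post-dose moments, with no rule for the intervals, cannot establish it. This does not depend on any assumption about episode length.

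The size of any power loss is conditional. With any-time rates and equal capture in both arms, exact Fisher power goes from 82.5–84.0% to 77.1–78.5% at 90% capture, 70.3–72.5% at 80% and 61.8–64.9% at 69%. There is no loss if the rates are visit-based, and less or none if RBT-9 shortens oxygen episodes. The capture fractions, episode lengths and baseline-oxygen shares are all assumptions, so these figures are a sensitivity range, not a demonstrated shortfall. The endpoint definition should be settled before any efficacy or futility look.

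**What to change.** 1. Define the primary endpoint as the worst WHO category on any day after dosing through Day 28. Derive it from dated oxygen, ventilation, admission/discharge and death records. Add explicit oxygen start and stop fields to the eCRF, which the oxygen-free-day endpoint needs anyway.
2. Keep the scheduled scores for the Wilcoxon comparison.
3. Pre-specify how subjects in category 4 at baseline or Day 1 are counted. One option is to adjust for baseline category and add a sensitivity analysis in subjects not on oxygen at baseline.
4. State in Section 11.6 whether the 25–38% and 10–20% rates are any-time or visit-based, and show power over a range of capture fractions if they do not match the final definition.

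The cost is slightly more data entry and a written derivation rule. The assumed rates may also need restating, and the power with them.

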## **10 ADVERSE EVENT REPORTING**

All adverse events will be recorded on the designated study eCRF for each subject beginning with the first administration of investigational product and ending with the date of the end of study visit (Day 28). Any unresolved adverse events will be followed by the Investigator until event resolution, the subject is lost to follow-up, or the adverse event is otherwise explained or not considered clinically significant by the Investigator. If the adverse event is ongoing on Day 28, it will be followed until Day 42 ( $\pm 4$ ). If the adverse event is ongoing on Day 42, it will be followed until Day 56 ( $\pm 4$ ), at which point it will be considered ongoing if not resolved.

#### **10.1 Investigator Reporting Requirements**

The Investigator must immediately report (within 24 hours by telephone and followed by a written report sent by fax or e-mail) all serious adverse events to the Sponsor, regardless of whether the Investigator believes that they are drug related, including those

events listed in the protocol as anticipated to occur in the study population independent of drug exposure (see [Section 10.2](#)).

These serious adverse events must be reported to:

[name], FASN, FNKF, FCRS  
Medical Monitor

Renibus Therapeutics, Inc.  
[name]  
[name]

[contact]  
[contact]  
E-mail: [contact]

Because the Investigator is knowledgeable about the human subject (eg, medical history, concomitant medications), administers the investigational drug, monitors the subject's response to the drug, is aware of the subject's clinical state and thus may be sensitive to distinctions between events due to an underlying disease process versus events that may be drug-related, and may have observed the event, the Investigator must include an assessment of causality (ie, whether there is a reasonable possibility that the drug caused the event) in the report to the Sponsor. Copies of each report to the Sponsor will be kept in the Investigator's study file.

The Investigator is responsible for complying with their IRB's requirements for reporting serious adverse events. Any expedited safety report (ie, serious unexpected suspected adverse reaction) received from the Sponsor should be submitted to the IRB. Copies of each report and documentation of IRB notification will be kept in the investigator's study file.

The Investigator must record non-serious adverse events in the eCRF and report them to Sponsor according to the timetable for reporting (eg, end of study).

